10.13.3. Study Intervention

If the safety of a trial participant is at risk because they cannot complete required evaluations or adhere to critical mitigation steps, then discontinuing that participant from study intervention must be considered.

Study intervention may be shipped by courier to study participants if permitted by local regulations and in accordance with storage and transportation requirements for the study intervention. Pfizer does not permit the shipment of study intervention by mail. The tracking record of shipments and the chain of custody of study intervention must be kept in the participant's source documents/medical records.

10.13.4. Home Health Visits

A home health care visit may be performed to facilitate scheduled visits per the Schedule of Activities. Home health visits include a healthcare provider conducting an in-person study visit at the participant's location, rather than an in-person study visit at the site. The following may be performed during a home health visit:

- Review and record study intervention(s), including compliance and missed doses.
- Review and record any AEs and SAEs since the last contact. Refer to [Section 8.3](#).
- Review and record any new concomitant medications or changes in concomitant medications since the last contact.
- Physical exam and targeted physical exam.
- Clinical AD assessments.
- Vital sign measurements.
- Review and record contraceptive method and results of pregnancy testing. Confirm that the participant is adhering to the contraception method(s) required in the protocol. Refer to [Appendix 4](#) and [Section 8.2.10](#) of this appendix regarding pregnancy tests.

- Review Patient-Reported Outcomes (PROs) and C-SSRS.
- Skin punch biopsy, **CCI** [REDACTED] could be performed by qualified personnel at their discretion.

10.13.5. Adverse Events and Serious Adverse Events

If a participant has COVID-19 during the study, this should be reported as an adverse event (AE) or serious adverse events (SAE) and appropriate medical intervention provided. Temporary discontinuation of the study intervention may be medically appropriate until the participant has recovered from COVID-19.

It is recommended that the investigator discuss temporary or permanent discontinuation of study intervention with the study medical monitor.

10.13.6. Efficacy Assessments

The IGA and EASI efficacy assessments may be assessed by a qualified rater as part of a home health care visit, but cannot be completed as part of a TeleHealth visit.

PROs may be completed as part of a home health care visit or a TeleHeath visit.

10.13.7. Independent Oversight Committees

The Data Monitoring Committee will be informed of considerations during Public Health Emergencies such as COVID-19 that may impact participant participation, participant safety, or study operations.

1. VERSION HISTORY

This is the first amendment of the Statistical Analysis Plan (SAP) for Study B7451037 and is based on the final protocol dated 12NOV2020.

Table 1. Summary of Changes

Version/Date	Associated Protocol Amendment	Rationale	Specific Changes
1 15 Oct 2019	Protocol Amendment 1 05 Sep 2019	N/A	N/A
2 29 Mar 2021	Protocol Amendment 3 12 Nov 2020	Due to lack of assay of sufficient quality to study immature fraction.	Section 2.1, 3.3.1, 4.3.1: Deleted “immature platelet fraction” and changed “platelet volume” to “platelet count, red blood cell count and reticulation”.
		For clarification and to add metabolites.	Section 2.1: Updated PK objectives/endpoints.
		Suggestion by SciOps for clarification.	Section 5.1: Added text to require baseline and a 12-week assessment.
		To allow for flexibility in analytical device.	Section 5.2.2: Deleted text “by Illumina HiSeq 2500”.
		An interim analysis has been added.	Section 7: Added text for interim analysis on the first 15 completers of the trial.
		Hypothetical estimands are not the best approach in this case.	Section 5.1.1 and 5.2.1: Deleted all references to a hypothetical estimand.
		Align with supplemental SAP.	Section 5.2.2: Remove RNA analyses since they will be part of the supplementary biomarker SAP.
3 8 Sep 2021	Protocol Amendment 3 12 Nov 2020	Clarify dose compliance derivation.	Section 6.7.3: Added detailed derivation for dose compliance.

2. INTRODUCTION

This SAP provides the detailed methodology for summary and statistical analyses of the data collected in Study B7451037. This document may modify the plans outlined in the protocol; however, any major modifications of the primary endpoint definition or its analysis will also be reflected in a protocol amendment.

2.1. Study Objectives

Study objectives and corresponding endpoints are provided in the Table 2 below.

[figure not shown]
Table 2 Study Objectives and Endpoints

Primary Objective:	Primary Endpoint:
To assess the PF-04965842 on lesional and non-lesional skin biomarkers of adult participants with moderate to severe atopic dermatitis (AD).	
 Changes from baseline in AD biomarkers in skin, including biomarkers for general inflammation (MM12), hyperplasia (K16), Th2 immune response (CCL17, CCL18, CCL26) and Th22 immune response (S100A8, S100A9, S100A12).
Secondary Objectives:	Secondary Endpoints:
To evaluate the effect of PF-04965842 on gene expression (evaluated by mRNA PCR and/or gene arrays).	
 Changes from baseline in gene expression (evaluated by mRNA PCR and/or gene arrays) over time in skin lesions.
To evaluate the effect of PF-04965842 on inflammatory infiltrates (T-cell and dendritic cells) using immunohistochemistry (IHC) in skin biopsies.	
 Changes from baseline in cellular (T-cells and dendritic cells) markers using IHC in skin biopsies at various time points.
To evaluate the effect of PF-04965842 on epidermal hyperplasia using IHC and RT PCR in skin biopsies.	
 Changes from baseline in hyperplasia markers (thickness, K16, Ki67) in skin biopsies.
To assess the effect of PF-04965842 on blood biomarkers (OLINK proteomic in serum).	
 Changes from baseline in blood biomarkers (OLINK proteomic microassay for inflammation and immune response in serum).
To assess changes in T-cell lymphocyte subset populations in blood using flow cytometry.	
 Changes from baseline in T-cell lymphocyte subset populations in blood using flow cytometry.
To evaluate the effect of PF-04965842 on pruritus and its correlation to IHC and genetic markers in lesional skin.	
 Response based on at least 4 points improvement in the severity of Peak Pruritus numerical rating scale (NRS) from baseline and change from baseline in IHC and genetic markers in lesional skin.
Efficacy Objectives:	Efficacy Endpoints:
To evaluate the effect of PF-04965842 on clinical efficacy outcomes.	
 Response based on the Investigator's Global Assessment (IGA) score of clear (0) or almost clear (1) on a 5 point scale and a reduction from baseline of ≥ 2 points at all scheduled time points. Response based on the Eczema Area and Severity Index $\geq 75\%$ improvement from baseline (EASI-75) response at all scheduled time points. Response based on at least 4 points improvement in the severity of Peak Pruritus NRS from baseline at all scheduled time points. Response based on a $\geq 50\%$ and $\geq 90\%$ improvement in the EASI total score (EASI-50 and EASI-90) at all scheduled time points.

	
 Change from baseline in the percentage Body Surface Area (BSA) affected at all scheduled time points.
Safety Objectives	Safety Endpoints
To evaluate the safety and tolerability of PF-04965842 during 12 weeks of treatment.	
 Incidence of treatment-emergent adverse events (TEAEs). Incidence of serious AEs (SAEs). Incidence of AEs leading to discontinuation. Incidence of clinical abnormalities and changes from baseline in clinical laboratory values, and vital signs.
Tertiary/Exploratory Objectives	Tertiary/Exploratory Endpoints
CCI	[REDACTED]
To assess the effect of PF-04965842 on Night Time Itch.	
 Changes from baseline in the Night Time Itch Scale at all scheduled time points.
CCI	[REDACTED]
	[REDACTED]
	[REDACTED]
	[REDACTED]
	[REDACTED]

2.2. Study Design

This is a randomized, double-blind, placebo-controlled, parallel-group, Phase 2a study to investigate the mechanism of action of PF-04965842 by correlating efficacy outcomes with changes from baseline in key skin and blood biomarkers in adult participants ≥ 18 years of age with moderate-to-severe AD. Participants will be screened within 28 days prior to the first dose of study intervention to confirm study eligibility. A total of approximately 51 participants will be randomized in a 1:1:1 ratio to receive PF-04965842 200 mg QD, PF-04965842 100 mg QD, or matching placebo QD for 12 weeks. A study design schematic is presented in Figure 1.

Figure 1 Study Design Schematic

At the end of the 12-week study treatment, qualified participants will have the option to enter the long-term extension (LTE) Study B7451015. Participants discontinuing early from this study will undergo a 4-week off-treatment follow-up period.

Eligible participants will be randomized into 3 intervention groups in the study:

Group 1 (N=17): PF-04965842 200 mg QD taken orally for 12 weeks.

Group 2 (N=17): PF-04965842 100 mg QD taken orally for 12 weeks.

Group 3 (N=17): placebo QD taken orally for 12 weeks.

The total duration of participation in the study is up to 20 weeks, including up to 4 weeks for screening, 12 weeks study intervention, and a follow-up period of 4 weeks after study intervention (for those participants who do not enter the LTE study).

A full schedule of activities for the study is provided in Appendix 7.

Sample Size Determination

The sample size of this study is based on the objective to evaluate changes in key AD biomarkers in skin lesions, including biomarkers for general inflammation (MMP12),

hyperplasia (K16), Th2 (CCL17, CCL18, CCL26), and Th22 (S100A8, S100A9, S100A12) with PF 04965842 200 mg QD, PF 04965842 100 mg QD, and placebo.

A total sample of approximately 51 participants, with 17 participants randomized to PF-04965842 200 mg QD, 17 participants randomized to PF-04965842 100 mg QD, 17 participants randomized to matching placebo (1:1:1 randomization) is planned.

A sample size of 17 participants per treatment group would provide about 92% chance that the 95% CI for the mean fold-change (post-baseline relative to baseline) has a half-width of no more than 3.2 (which is within 64% of an assumed maximal standard deviation of 5 for the fold-change, as based on published data). Calculations are based on the assumption of a chi-square distribution for the variance so that the width of the estimated confidence interval is a random quantity.

3. ENDPOINTS AND BASELINE VARIABLES: DEFINITIONS AND CONVENTIONS

3.1. Primary Endpoints

The primary endpoints are:

- Changes from baseline in AD biomarkers in skin, including biomarkers for general inflammation (MMP12), hyperplasia (K16), Th2 immune response (CCL17, CCL18, CCL26), and Th22 immune response (S100A8, S100A9, S100A12).

3.2. Secondary Endpoints

The secondary endpoints are:

- Changes from baseline in gene expression (evaluated by mRNA PCR and/or gene arrays) over time in skin lesions;
- Changes from baseline in cellular (T cells and dendritic cells) markers using IHC in skin biopsies at various time points;
- Changes from baseline in hyperplasia markers (thickness, K16, Ki67) in skin biopsies;
- Changes from baseline in blood biomarkers (OLINK proteomic microassay for inflammation and immune response in serum);
- Changes from baseline in T cell lymphocyte subset populations in blood using flow cytometry;
- Change from baseline in IHC and genetic markers in lesional skin.

A detailed description of how the pruritus NRS score is derived is provided in Appendix 3.

3.3. Secondary Efficacy Endpoints

The secondary efficacy endpoints are:

- Response based on the Investigator's Global Assessment (IGA) score of clear (0) or almost clear (1) (on a 5 point scale) and a reduction from baseline of ≥ 2 points at all scheduled time points;
- Response based on the Eczema Area and Severity Index $\geq 75\%$ improvement from baseline (EASI 75) response at all scheduled time points;
- Response based on at least 4 points improvement in the severity of Peak Pruritus NRS from baseline at all scheduled time points;
- Response based on a $\geq 50\%$ and $\geq 90\%$ improvement in the EASI total score (EASI-50 and EASI-90) at all scheduled time points;
- Change from baseline in the percentage Body Surface Area (BSA) affected at all scheduled time points.

3.3.1. Tertiary/Exploratory Endpoints

- CCI
[REDACTED]
- Changes from baseline in Night Time Itch Scale at all scheduled time points;
- CCI
[REDACTED]
- [REDACTED]
- [REDACTED]
- [REDACTED]
- [REDACTED]

3.4. Baseline Variables

In general, for all analyses, baseline will be defined based on observations collected prior to first dose. Baseline values for demographics, medical and other history, atopic dermatitis history will be based on measures collected at Visit 1/Screening visit. Study Day 1 is defined as the day the subject receives first dose of study drug. For purposes of all other analyses including analyses for change from baseline, the baseline value will be defined as measured on Day 1 (before time of first dose, if time

is available). If a value is missing on Day 1, then the last available observation before Day 1 will be used.

3.5. Safety Endpoints

Safety will be assessed by the spontaneous reporting of AEs, physical examinations, and clinical laboratory results in all subjects who receive at least one dose of the investigational product. Unscheduled safety assessments may be performed at any time during the study to assess any perceived safety concerns. Endpoints will be assessed as:

- Incidence of treatment emergent adverse events (AEs) and serious AEs (SAEs).
- AEs leading to discontinuation.
- Serious infections, defined as any infection (viral, bacterial, and fungal) requiring hospitalization or parenteral antimicrobials or met other criteria that required the event be classified as serious;
- Incidence of clinical abnormalities and change from baseline in selected clinical laboratory values, ECG measurements, and vital signs.

The safety endpoints will be defined in accordance with Clinical Data Interchange Standards Consortium (CDISC) aligned Pfizer Standards (CaPS).

3.5.1. Adverse Events

An adverse event will be considered a Treatment-Emergent Adverse Event (TEAE) if the event started during the effective duration of treatment. All events that start on or after the first dosing day and time/start time, if collected, but before the last dose plus the lag time (28 days) will be flagged as TEAEs. The algorithm will not consider any events that started prior to the first dose date.

3.5.2. Laboratory Data

Below is a list of hematology and serum chemistry test parameters.

- Hematology: hemoglobin, hematocrit, red blood cell count, red blood cell indices (MCV, MCH, MCHC, RBC morphology), reticulocyte count, platelet count, white blood cell count with differential, total neutrophils, eosinophils, monocytes, basophils, lymphocytes, coagulation panel.
- Clinical chemistry: blood urea nitrogen, creatinine, creatine phosphokinase, glucose (non-fasting, Day 1 and Week 12 fasting), sodium, potassium, chloride, calcium, total bicarbonate, aspartate aminotransferase, alanine aminotransferase, gamma-glutamyl transferase, bilirubin, alkaline phosphatase, lactate dehydrogenase, uric acid, albumin, total protein, total cholesterol, low-density lipoprotein (LDL), high-density lipoprotein (HDL), triglycerides.

Below is a list of urinalysis test parameters

- pH, glucose, protein, blood, ketones, nitrite, leukocyte esterase by dipstick;
- Microscopic examination and/or culture.

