1.2. Schema

1.3. Schedule of Activities (SoA)

	Screening	Intervention Period										Follow-up	Notes
Visit Identifier	Day -28	Day 1 Week 0 Base line	Day 2 Week 0	Day 4 Week 0	Day 8 Week 1 (by Phone)	Day 15 Week 2	Day 29 Week 4	Day 43 Week 6	Day 57 Week 8	Day 85 Week 12 (EOT/ET)	Day 113 Week 16 (EOS)	Visit 11 is 4 weeks after last dose in case of early study termination.	
	Visit 1	Visit 2	Visit 3	Visit 4	Visit 5	Visit 6	Visit 7	Visit 8	Visit 9	Visit 10	Visit 11		
Visit Window (days)	None	None	None	±1	±1	±1	±2	±3	±3	±3	±3		
Enrollment Procedures													
Informed consent	X												
Register participant using IRT	X											See Section 6.3	
Inclusion and exclusion criteria	X	X										See Section 5.1 and Section 5.2	
Demographics, medical history, tobacco and alcohol history, AD disease history and prior AD treatments	X											See Section 8.2.1	
Review prior/concomitant medications & treatments	X	X	X	X	X	X	X	X	X	X	X		

	Screening	Intervention Period											Follow-up	Notes
Visit Identifier	Day -28	Day 1 Week 0 Base line	Day 2 Week 0	Day 4 Week 0	Day 8 Week 1 (by Phone)	Day 15 Week 2	Day 29 Week 4	Day 43 Week 6	Day 57 Week 8	Day 85 Week 12 (EOT/ET)	Day 113 Week 16 (EOS)	Visit 11 is 4 weeks after last dose in case of early study termination.		
	Visit 1	Visit 2	Visit 3	Visit 4	Visit 5	Visit 6	Visit 7	Visit 8	Visit 9	Visit 10	Visit 11			
Provide patient emergency contact card	X													
Medical Procedures														
Complete physical examination	X									X		See Section 8.2.1		
Targeted physical exam		X				X	X		X		X			
Vital signs (blood pressure, pulse rate, respiratory rate, temperature)	X	X				X	X		X	X	X	See Section 8.2.2		
Weight	X									X		See Section 8.2.1		
Height	X											See Section 8.2.1		
Chest X-Ray	X											See Section 8.2.3		
ECG (12-lead)	X											See Section 8.2.7		
Laboratory Procedures														

	Screening	Intervention Period										Follow-up	Notes
Visit Identifier	Day -28	Day 1 Week 0 Base line	Day 2 Week 0	Day 4 Week 0	Day 8 Week 1 (by Phone)	Day 15 Week 2	Day 29 Week 4	Day 43 Week 6 (by Phone)	Day 57 Week 8	Day 85 Week 12 (EOT/ET)	Day 113 Week 16 (EOS)	Visit 11 is 4 weeks after last dose in case of early study termination.	
	Visit 1	Visit 2	Visit 3	Visit 4	Visit 5	Visit 6	Visit 7	Visit 8	Visit 9	Visit 10	Visit 11		
Serum chemistry	X	X				X	X		X	X	X	See Appendix 2 . See Section 8.2.8 for guidance on abnormal lab results	

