5.3.1. Meals and Dietary Restrictions

On study visit days (Day 1 and Week 12), participants must comply with fasting requirements for at least 8 hours prior to the visit. Water and permitted non-study medications are allowed ([Section 8.2.8](#)).

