8. STUDY ASSESSMENTS AND PROCEDURES

- Study procedures and their timing are summarized in the [Schedule of Activities](#). Protocol waivers or exemptions are not allowed.
- Immediate safety concerns should be discussed with the sponsor immediately upon occurrence or awareness to determine if the participant should continue or discontinue study intervention.
- Adherence to the study design requirements, including those specified in the [Schedule of Activities](#), is essential and required for study conduct.
- All screening evaluations must be completed and reviewed to confirm that potential participants meet all eligibility criteria. The investigator will maintain a screening log to record details of all participants screened and to confirm eligibility or record reasons for screening failure, as applicable. Participants will be screened (Visit 1) within 28 days prior to administration of the study intervention to confirm that they meet the participant selection criteria for the study. The investigator (or an appropriate delegate at the investigator site) will obtain informed consent from each participant, in accordance with the procedures described in [Section 10.1.3](#).
- Procedures conducted as part of the participant's routine clinical management (eg, blood count) and obtained before signing of the ICF may be utilized for screening or baseline purposes provided the procedures met the protocol-specified criteria and were performed within the time frame defined in the [Schedule of Activities](#).
- Screening laboratory tests with abnormal results may be repeated once to confirm abnormal results; the last value will be used to determine eligibility. If results return to normal within the 4-week screening period, the participant may enter the study.
- Due to possible need for PPD testing and chest radiograph, screening procedures may be performed over more than 1 visit in the 28 days prior to the Day 1 visit.
- Visit windows are based on Day 1 visit. To assure consistency and reduce variability, all study visits should occur in the morning whenever possible. On days of study visits, participants will receive their dose at the clinic during the visit.
- Participants are required to fast for at least 8 hours prior to all visits that include lipid profile panel testing (Day 1 and Week 12). During the fasting period, participants should refrain from all food and liquids (water and permitted non-study medications are allowed).

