8.2.8. Clinical Safety Laboratory Assessments

- See [Appendix 2](#) for the list of clinical laboratory tests to be performed and the *Schedule of activities* for the timing and frequency.
- Participants must abstain from all food and drink (except water and non-study medications) for an 8-hour overnight fast prior to labs that include the lipid profile panel on Day 1 and Week 12. All other labs do not require fasting.
- Sample collection, labeling, storage, and shipping information can be found in the laboratory manual.
- The investigator must review the laboratory report, document this review, and record any clinically relevant changes occurring during the study in the AE section of the CRF. The laboratory reports must be filed with the source documents. Clinically significant abnormal laboratory findings are those which are not associated with the underlying disease, unless judged by the investigator to be more severe than expected for the participant's condition.
- All laboratory tests with values considered clinically significantly abnormal during participation in the study or within 28 days after the last dose of study intervention should be repeated until the values return to normal or baseline or are no longer considered clinically significant by the investigator or medical monitor.
 - If such values do not return to normal/baseline within a period of time judged reasonable by the investigator, the etiology should be identified and the sponsor notified.
 - All protocol-required laboratory assessments, as defined in [Appendix 2](#), must be conducted in accordance with the laboratory manual and the [Schedule of Activities](#).
 - If laboratory values from non-protocol specified laboratory assessments performed at the institution's local laboratory require a change in participant management or are considered clinically significant by the investigator (eg, SAE or AE or dose modification), then the results must be recorded in the CRF.

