10.2. Appendix 2: Clinical Laboratory Tests

- The tests detailed in [Table 7](#) will be performed by the central laboratory.
- Local laboratory results are only required in the event that the central laboratory results are not available in time for either study intervention administration and/or response evaluation. If such a local sample is required, it is important that the sample for central analysis is obtained at the same time. Additionally, if the local laboratory results are used to make either a study intervention decision or response evaluation, the results must be entered into the CRF. This is applicable for repeat tests.
- Protocol-specific requirements for inclusion or exclusion of participants are detailed in section [5](#) of the protocol.
- Additional tests may be performed at any time during the study as determined necessary by the investigator or required by local regulations.
- Pregnancy Testing
 1. Refer to [Section 5.1](#) Inclusion Criteria and [Section 8.2.10](#) Pregnancy Testing for screening pregnancy criteria.
 2. For details of timing of recommended pregnancy testing see the [Schedule of Activities](#).

Table 7. Protocol-Required Safety Laboratory Assessments

Laboratory Assessments	Parameters			
Hematology	CCI [REDACTED] Hemoglobin Hematocrit	RBC Indices: MCV MCH MCHC RBC Morphology Reticulocyte Count	White blood cell (WBC) count with Differential: Total Neutrophils Lymphocytes Monocytes Eosinophils Basophils Coagulation Panel Activated Partial Thromboplastin Time (APTT) Prothrombin Time/International Normalized Ratio (PT/INR)	
Clinical Chemistry ¹	Blood urea nitrogen (BUN) Creatinine Creatine Phosphokinase Glucose (non-fasting) (Day 1 and Week 12 fasting) AST	ALT GGT Potassium Sodium Calcium	Chloride Uric acid Albumin Total Protein Total CO2 (bicarbonate)	Total, indirect and direct bilirubin Alkaline phosphatase Lactate dehydrogenase
Lipid Profile Panel ¹	Total cholesterol	Triglycerides	LDL	HDL
Routine Urinalysis	
 pH, glucose, protein, blood, ketones, nitrite, leukocyte esterase by dipstick Microscopic examination and/or culture² 			
Other Tests ⁹	
 HIV³ HBsAg³ HBcAb³ HBsAb^{3,4} HBV DNA⁵ HCVAb^{3,4} HCV RNA^{3,4} Viral test at baseline Serum Pregnancy Test^{3,6} Urine pregnancy test⁶ QFT-G or PPD (if applicable)⁷ CCI [REDACTED] Lymphocyte Subsets Total T cells (CD3+) CD4+ T cells (CD3+CD4+)			

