6.8. Safety Summaries and Analyses

Safety analyses will be based on the SAF analysis set.

All clinical AEs, SAEs, TEAEs, withdrawal due to AEs, ECGs, vital signs and safety laboratory data will be reviewed and summarized on an ongoing basis during the study to evaluate the safety of subjects.

Safety data will be presented in tabular and/or graphical format and summarized descriptively, where appropriate. All safety endpoints will be listed and summarized in accordance with CaPS. Categorical outcomes (eg, AEs) will be summarized by subject counts and percentage. Continuous outcome (eg, blood pressure, pulse rate, etc.) will be summarized using N, mean, median, standard deviation, etc. Change from baseline in laboratory data, ECGs and vital signs will also be summarized. Subject listings will be produced for these safety endpoints accordingly.

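### Planned glucose change from baseline sets a fasting Day 1 value against draws that need not be fasting at Weeks 2, 4 and 8, which would tend to show an artefactual rise in every arm

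*SAP*

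**What the plan says.** The two documents agree on how glucose is drawn. SAP 3.5.2 has "glucose (non-fasting, Day 1 and Week 12 fasting" and Protocol Appendix 2 (Table 7) has "Glucose (non-fasting) (Day 1 and Week 12 fasting". Protocol 5.3.1 supplies the fasting rule: "On study visit days (Day 1 and Week 12), participants must comply with fasting requirements for at least 8 hours prior to the visit". For everything outside the lipid visits, Protocol 8.2.8 states "All other labs do not require fasting".

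The "Serum chemistry" row of the Schedule of Activities is marked at Screening, Day 1 and Weeks 2, 4, 8, 12 and 16.

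On the analysis side, SAP 3.4 says "the baseline value will be defined as measured on Day 1", pre-dose where the time is known, and falls back to the last earlier observation when Day 1 is missing. SAP 6.8 says "Change from baseline in laboratory data, ECGs and vital signs will also be summarized". SAP 6.8.2 adds only a reference to the sponsor's reporting standards and a summary of monitoring and discontinuation criteria. SAP 6 keeps Week 16 data to listings. I find no text in either document that separates fasting from non-fasting glucose in the summaries, or that limits the glucose change to particular visits.

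**The concern.** A change from baseline is interpretable when both measurements are taken under the same conditions. For glucose the plan fixes the condition at baseline (at least 8 hours fasted) and at Week 12, and leaves it open at the visits between. The change at Weeks 2, 4 and 8 then carries meal status as well as anything treatment does.

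The expected pattern is a rise at Weeks 2 to 8 that goes away at Week 12. Someone reading down one arm of a descriptive safety table could take that for a transient metabolic effect. Changes from baseline in laboratory values are a stated safety endpoint (Protocol Section 3; SAP Table 2), so the table is not incidental. The stake is the readability of one descriptive safety summary. No primary, secondary or efficacy result depends on it.

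**Working it through.** The plan states no figure on this point, so there is nothing to reproduce. The check is a trace of draw conditions through the schedule, followed by a bound on size under stated assumptions.

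**Step 1. Draw condition by visit**

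| Visit | Chemistry drawn | Fasting required | Use in the change summary |
|---|---|---|---|
| Screening | yes | no | baseline only if Day 1 is missing |
| Day 1 | yes | yes | baseline |
| Weeks 2, 4, 8 | yes | no | change = fasting not required minus fasting |
| Week 12 | yes | yes | change = fasting minus fasting |
| Week 16 | yes | no | listing only |

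Analysed on-treatment visits are Weeks 2, 4, 8 and 12. The conditions match at 1 of 4 and differ at 3 of 4.

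**Step 2. Expected artefact in an arm's mean change**

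Let *f* be the share of participants who ate before the visit and *d* the fed-minus-fasting shift. With no drug effect, the expected mean change is *f* × *d*. Neither quantity is in the documents. I assume *f* from 0 to 100% and *d* from 0.2 to 2.0 mmol/L.

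| Share fed | d = 0.2 | d = 0.5 | d = 1.0 | d = 2.0 |
|---|---|---|---|---|
| 0% | 0 | 0 | 0 | 0 |
| 50% | 0.10 | 0.25 | 0.50 | 1.00 |
| 100% | 0.20 | 0.50 | 1.00 | 2.00 |

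**Step 3. Would it be visible with 17 per arm?**

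Take an assumed SD of 0.8 mmol/L for the change, and no drug effect. Mixed feeding adds variance *f*(1 − *f*)*d*². The standard error of an arm mean is √[(0.64 + *f*(1 − *f*)*d*²)/17], and the chance that all three arm means are above zero is Φ(*fd*/SE)³.

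- *f* = 0: 0.5³ = 0.125 (simulation 0.13).
- *f* = 50%, *d* = 0.5: SE = √(0.7025/17) = 0.203; 0.25/0.203 = 1.23; probability 0.71.
- *f* = 50%, *d* = 1.0: SE = √(0.89/17) = 0.229; 0.50/0.229 = 2.19; probability 0.96.
- *f* = 100%, *d* = 0.5: SE = 0.8/√17 = 0.194; 0.50/0.194 = 2.58; probability 0.985.
- *f* = 100%, *d* = 1.0: probability 1.00.

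A simulation of 20,000 trials per scenario gives the same values.

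**Step 4. Active versus placebo**

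Meal status before a visit is not tied to the blinded assignment, so *f* × *d* has the same expectation in each arm and cancels. The simulated mean difference was within 0.004 mmol/L of zero in every scenario. What remains is some extra noise: with *f* = 50% and *d* = 1.0, the SD of a difference between two arm means goes from √(2 × 0.64/17) = 0.27 to √(2 × 0.89/17) = 0.32 mmol/L.

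**Step 5. Missing Day 1**

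The SAP 3.4 fallback then uses a screening glucose for which fasting was not required. For that participant the fasting Week 12 value is compared with a possibly fed baseline, and the error tends downward. One such participant out of 17, fed at screening with *d* = 1.0, moves the arm's Week 12 mean by −1.0/17 = −0.06 mmol/L.

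**The case against.** **Fed status is not known.** The protocol does not require fasting at Weeks 2, 4 and 8, but it does not require eating either, and "all study visits should occur in the morning whenever possible". Some participants may arrive fasted. This stands. A reader might infer a certain false rise in every arm; the documents support only a tendency, which may be zero. Mixed fed status does not repair the comparison, because the change still combines meal status with treatment.

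**There is a concurrent placebo arm.** The artefact should appear there too, with an expected difference of zero, and safety is summarised without formal testing. This stands and limits the harm to within-arm reading. A reader might infer a biased drug-placebo contrast; nothing in the plan supports that.

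**The sponsor's reporting standards may already deal with it.** SAP 3.5 speaks of *selected* laboratory values, and SAP 6.8.2 defers to standards that are not part of these documents. That leaves open what the final table will look like. It does not remove the mismatch in the plan: SAP 3.5.2 lists glucose, and the endpoint in SAP Table 2 and the sentence in SAP 6.8 carry no such qualifier.

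**High-glucose flags.** A reader might also infer that counts of high values are inflated at the non-fasting visits. The documents give no glucose limit or flag, and the monitoring and discontinuation criteria in Protocol Appendix 10 contain none for glucose, so the point cannot be made from them.

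**Conclusion.** The mismatch is real and follows from the text alone: 3 of the 4 analysed on-treatment glucose changes compare a draw where fasting was not required with a fasting baseline. The effect would tend to be an artefactual within-arm rise at Weeks 2, 4 and 8 in all arms, with Week 12 unaffected unless the baseline came from screening.

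The size cannot be taken from the documents. Under the assumed ranges it runs from 0 to 2.0 mmol/L, and whether all three arms of 17 show it depends on the share fed, the shift and an assumed SD of 0.8 mmol/L. The expected active-versus-placebo difference is zero throughout. The missing-baseline route affects only participants without a Day 1 value, and the documents give no frequency for that. The issue is confined to a descriptive safety table, but it is worth correcting because the correction is nearly free.

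**What to change.** In SAP 6.8.2:

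- Summarise change from baseline in glucose only at Week 12, against a fasting Day 1 value.
- Report Weeks 2, 4 and 8 as observed values by arm, labelled non-fasting.
- For glucose, do not let a screening value drawn without a required fast replace a missing fasting Day 1 value under the SAP 3.4 fallback; leave the change missing for that participant.

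Change from the screening value is not a sound substitute for the Week 2, 4 and 8 comparison. Meal status at screening is equally uncontrolled, and the sample may be taken up to 28 days before dosing, while systemic corticosteroids or other atopic dermatitis treatments are being washed out (Protocol 4.1 and 5.2).

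The cost is SAP wording and one programming rule, with no new data. The downside is a glucose change table with one post-baseline visit in place of four, and the loss of a Week 12 change for any participant without a fasting Day 1 value.
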